6.20.7. Pulmonary Function Tests

Pulmonary function tests (PFTs) including FEV₁, FVC, and DLCO, if applicable, measurements will be performed as scheduled in the protocol. These tests will be performed at a high qualified pulmonary function laboratory or respiratory department.

A minimum of 3 acceptable maneuvers will be performed at each visit. The acceptability criteria are a satisfactory start of test and a satisfactory end of test. The largest FVC and the largest FEV_1 will be recorded, after examining the data from all of the acceptable curves, even if the 2 values do not come from the same curve.

For FEV1 and FVC, summary tables for actual value, change, percent change, percent predicted, change in percent predicted, and percent change in percent predicted will be produced. For DLCO summary tables for actual value, change, and percent change will be produced. DLCO is collected at the local lab

for each site, so results may be collected in domestic or SI units. DLCO results in domestic units (mL/min/mmHg) will be converted to SI units (mmol/min/kPa) prior to analysis using the following conversion factor: DLCO in SI units = (DLCO in domestic units) / 2.986.

Line plots of FEV1, FVC, and DLCO results over time will be presented. PFT test results will also be listed.

6.20.8. Ophthalmological Examination

Optical Coherence Tomography (OCT) will be performed at scheduled times as outlined in protocol.

Any clinically significant changes will be recorded as AEs or SAEs. OCT details will also be listed.

6.20.9. Dermatological Examination

Dermatological evaluations will be performed Screening, the End of Study Visit, Visit 10LP, and the End of OLP Visit as part of the physical examination.

A certified dermatologist will perform dermatological evaluations if abnormal results are found on the physical examination. Any clinically significant changes will be recorded as AEs or SAEs. Dermatological examination abnormalities by visit will be presented and dermatological examination details will be listed.

6.21. PD Analysis

In addition to summarizing the actual values and change from baseline in Absolute lymphocyte count (ALC) specified as part of the Hematology analysis, percent change in ALC will also be summarized by treatment group. Actual value, change, and percent change in ALC over time will also be plotted.

7. REPORTING CONVENTIONS

The following reporting conventions will be adopted for the tables, listings, and figures. These conventions will enhance the review process and help to standardize presentation with common notations.

- All tables and data listings will be presented in Landscape Orientation, unless presented as part of the text in a CSR, in Courier New, 10 point font.
- Figures will be presented in Landscape Orientation, unless Portrait Orientation suggests that the information presented is easier to interpret.
- Legends will be used for all figures with more than one variable or item displayed.
- Lines should be wide enough to see the line after being copied.
- Specialized text styles, such as bolding, italics, borders, shading text will not be used in tables, figures, and data listings unless they add significant value to the table, figure, or data listing.
- Only standard keyboard characters should be used in tables and data listings. Special
 characters, such as non-printable control characters, printer specific, or font specific
 characters, will not be used on a table, figure, or data listing. Hexadecimal characters are
 allowed (e.g., μ,α,β).
- Capital letters will be used throughout all tables, figures, and data listings.
- A standard header on each page will contain information to include the sponsor name ("Receptos, Inc.") and study identifier ("Protocol RPC01-202").
- The ICH numbering convention will be used for all tables, listings, and figures.
- All footnotes will be left justified and at the bottom of a page.
- Missing values (other than date values) for both numeric and character variables will be presented as blanks in a table or data listing. Missing date/month/year will be presented as dash ('-') for each space.
- All date values will be presented as DDMMMYYYY (e.g., 29AUG2009) format. A four-digit year is preferred for all dates.
- All observed time values will be presented using a 24-hour clock HH:MM format (e.g., 01:35). Seconds should only be reported if they were measured as part of the study.
- Time durations will be reported in mixed HHh MMm notation (e.g., 5h 32m). The use of decimal notation to present time durations should be avoided (e.g., 0.083h = 5m) unless it is necessary to show the computation of time differences in a table, figure, or data listing, in which case both notations may be used to display the time duration.
- All tables, figures, and data listings will have the name of the program and a date/time stamp on the bottom of each output.
- Each table, figure, and data listing will have "Page x of y" presented on the top right-hand side of each page.
- Additional rounding rules as follows:

- o If the original value has 0 decimal places: mean, median, and CIs will have one decimal place and SD will have 2 decimal places
- o If the original value has 1 decimal place: mean, median, and CIs will have 2 decimal places and SD will have 3 decimal places
- o If the original value has 2 or more decimal places: mean, median, CIs, and SD will all have 3 decimal places
- All calculated percentages between 1% and 99% will be rounded to one decimal place. A percentage of 100% will be reported as 100%. Any computation of percentage that results in 0% will be reported as 0 as the number of responses and no percentage will be reported. All categories whose counts are zero will be displayed for the sake of completeness.
- P-values will be rounded to four decimal places. If a p-value is less than 0.0001, it will be reported as "<0.0001". If a p-value is greater than 0.9999, it will be reported as ">0.9999".

8. DEVIATIONS FROM PROTOCOL

The analyses of the following endpoints specified in the protocol are not performed due to collected samples have not been analyzed at the time of database lock.

- Proportion of patients with histologic Remission at Week 8 for exploratory objectives and exploratory efficacy endpoints.
- Plasma protein biomarkers (cytokines, chemokines, other inflammatory proteins) as PD endpoint.

STATISTICAL ANALYSIS PLAN - OPEN LABEL PERIOD ADDENDUM

Title: A Phase 2, multi-center, randomized, double-blind, placebo-

controlled parallel-group study to evaluate the clinical efficacy and

safety of induction therapy with RPC1063 in patients with

moderately to severely active ulcerative colitis

Protocol: RPC01-202

Sponsor: Celgene International II Sàrl (see appended signature page)

[name] [name]

[contact]

Date: October 15, 2019

Status: Addendum to Version 2.0

CONFIDENTIAL

This document is a confidential communication of Receptos. Acceptance of this document constitutes agreement by the recipient that no unpublished information contained herein shall be published or disclosed without prior written approval, except that this document may be disclosed to the appropriate Institutional Review Board(s)/Independent Ethics

Committee(s) under the condition that they keep it confidential.

TABLE OF CONTENTS

SIGNA	ATURES	2
TABLE	E OF CONTENTS	3
LIST O	OF ABBREVIATIONS	4
1.	Introduction	5
2.	Study Design	5
3.	Analysis Cohorts	5
4.	DMC	5
5.	Patient Disposition	5
6.	OLP Baseline	5
7.	Efficacy Analyses	6
7.1.	Endpoints	6
7.2.	Mayo Score at the End of OLP	6
7.3.	Visit Windows	7
8.	Safety Analyses	8
9.	Guideline on Missing Date Imputation	8

LIST OF ABBREVIATIONS

AE adverse event DEF definition

DMC data monitoring committee

IP Induction Period ITT intent-to-treat

[figure not shown]
MP Maintenance Period

NRI Non-responder imputation
OLP Open-Label Treatment Period

SAE serious adverse event SAP statistical analysis plan

UC ulcerative colitis

1. Introduction

Study Design

3. Analysis Cohorts

- Intent-to-Treat (ITT) Analysis Cohorts will be labeled by randomized treatment in the parent study for all subjects who received at least one dose of RPC1063 1mg in OLP.
- Safety Analysis Cohorts will be labeled by actually received treatment in the parent study for all subjects who received east one dose of RPC1063 1mg in OLP.

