All patients who complete the IP and are responders (see [Section 13.8](#)) at Week 8 of the IP will enter the 24-week MP. Patients will continue to receive the same investigational drug in the MP as received during the IP, and individual patient treatment will remain blinded until all patients have reached Week 32. The last visit in the MP will occur at Week 32. Patients

who complete the MP will be given the option to participate in the OLP. Patients that enter the MP and experience disease relapse will have the option to enter the OLP.

Optional Open-Label Treatment Period (OLP)

Patients who complete the IP and are non-responders at Week 8 and those that complete the MP or experience disease relapse during the MP will have the option to enter the OLP. All patients in the OLP will receive daily study treatment with RPC1063 1 mg. There will be an 8-day dose escalation regimen consisting of 4 days of treatment with RPC1063 0.25 mg, followed by 3 days of treatment with RPC1063 0.5 mg, followed by RPC1063 1 mg.

Patients who have not shown clinical improvement 8 weeks after initiation of the OLP should discontinue from the study. Eligible patients will be transitioned into the Phase 3 open-label extension UC Study RPC01-3102 and will be able to immediately enter the study (without completing the 30-day or 90-day Safety Follow-up Visits). The OLP will continue for up to 6 years, or until marketing approval of RPC1063 for UC in the country of the clinical site (estimated to be in 2019), or completed transition of patients to Study RPC01-3102, or until the Sponsor discontinues the development program.

Safety Monitoring/Follow-up

Potential AEs of interest that may be a consequence of S1P₁ modulation will be closely monitored during the study. These AEs include bradycardia, heart conduction abnormalities, pulmonary toxicity, macular edema, cutaneous malignancy, serious or opportunistic infection, and hepatotoxicity. A DMC for the study will perform safety reviews periodically, approximately 4 times a year until the end of the Maintenance Period.

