13.5. Analysis Populations

The following analysis populations will be used in the statistical analysis:

Intent-to-Treat (ITT): The ITT population will consist of all randomized patients. The primary efficacy analysis will be carried out in the intent-to-treat population, with treatment assignment designated according to randomized treatment.

Modified Intent-to-Treat (MITT): The MITT population will consist of all randomized patients who received at least 1 dose of investigational drug, with treatment assignment designated according to randomized treatment.

Per Protocol (PP): The PP population will consist of the subset of the ITT population, excluding those patients who have had a major protocol violation. These will be defined prospectively, in advance of data lock and primary analyses, in the final SAP, by the (aggregate results blinded) project statistician.

PK: The PK population will consist of patients who have at least one baseline and one post-baseline PK assessment.

Safety: The Safety population will consist of all patients receiving any investigational drug and safety analyses will be carried out on this population according to treatment actually received.

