the MP will occur at Week 32. Patients who complete the MP will be given the option to participate in the OLP. Patients that enter the MP and experience disease relapse will have the option to enter the OLP.

Optional Open-Label Treatment Period (OLP)

Patients who complete the IP and are non-responders at Week 8 and those that complete the MP or experience disease relapse during the MP will have the option to enter the OLP. All patients in the OLP will receive daily study treatment with RPC1063 1.0 mg. There will be an 8 day dose titration regimen consisting of 4 days of treatment with 0.25 mg RPC1063, followed by 3 days treatment with RPC1063 0.5 mg, followed by RPC1063 1.0 mg. Patients who are non-responders 8 weeks after initiation of the OLP should discontinue from the study. The OLP will continue until the last patient who enters the OLP portion of the study has completed 20 weeks of treatment in the OLP.

[figure not shown]
Safety Monitoring/Follow-up

Potential adverse events (AEs) of interest that may be a consequence of sphingosine 1-phosphate 1 receptor 1 (S1P1R) modulation will be closely monitored during the study. These AEs include bradycardia and heart conduction abnormalities, pulmonary toxicity, macular edema, cutaneous malignancy, serious or opportunistic infection and hepatotoxicity. A Data Monitoring Committee (DMC) for the study will perform safety reviews periodically, approximately four times a year.

The safety of patients will be monitored by collection of treatment-emergent AEs, SAEs, physical exams, vital signs, Holter monitoring and ECGs, Pulmonary Function Tests (PFTs), optical coherence tomography (OCT), dermatologic exams, blood chemistry and hematology panels, coagulation panels, and urinalysis at baseline and at various time points during the study. White blood cell (WBC) counts and lymphocyte counts will be monitored centrally (and will not be provided to the site) to prevent potential unblinding of the Investigator.

Patients who discontinue from treatment due to lack of response, AEs, or other reasons, even if alternative treatment is given, will be followed for 30 days for collection of safety data, including lymphocyte recovery, and for the assessment of their disease status.

Figure 1: Study Schematic

5. **DEFINITIONS**

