5.4. Other Definitions

Age

Age (in years) will be calculated from the date of birth to the date of informed consent. Age will be reported as an integer.

Study Drug

Study drug refers to RPC1063 0.5 mg, RPC1063 1.0 mg, or Placebo oral capsules as well as the titration doses.

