7.3. Visit Windows

Post-OLP-Baseline visits (scheduled or unscheduled) during OLP will be mapped to an analysis visit based on the windowing algorithm below. If a visit cannot be mapped to any analysis visit, then the analysis visit will be set to missing and the data of interest will be excluded from summaries. If multiple visits containing the same data of interest can be mapped to the same analysis visit, the visit closest to the target day will be used in the analysis. In the event that two or more visits are equidistant to the target day, the later visit will be used in the analysis. If the two visits are on the same day, then the visit with the worst result will be used in the analysis.

Visit	Target Day	Analysis Visit Window for partial Mayo score	Analysis Visit Window for Complete Mayo Score, 9-point Mayo Score and Geboes Index
		(+/- 6 weeks)	(+/- 24 weeks)
Day 1OLP	1	N/A	N/A
Week 4OLP	36	(19-50)	N/A
Week 8OLP	64	(51 - 106)	N/A
Week 20OLP	148	(107 - 190)	N/A
Week 32OLP	232	(191 - 274)	N/A
Week 44OLP	316	(275 - 358)	N/A
Week 56OLP	400	(359 - 442)	(232 - 568)
Week 68OLP	484	(443 - 526)	N/A
Week 80OLP	568	(527 - 610)	N/A
Week 92OLP	652	(611 - 694)	N/A

Week 104OLP	736	(695 - 778)	(569 - 904)
Week 116OLP	820	(779 - 862)	N/A
Week 128OLP	904	(863 - 946)	N/A
Week 140OLP	988	(947 - 1030)	N/A
Week 152OLP	1072	(1031 - 1114)	(905 - 1240)
Week 164OLP	1156	(1115 - 1198)	N/A
Week 176OLP	1240	(1199 - 1282)	N/A
Week 188OLP	1324	(1283 - 1366)	N/A
Week 200OLP	1408	(1367 - 1450)	(1241 - 1576)
Week 212OLP	1492	(1451 - 1534)	N/A
Week 224OLP	1576	(1535 - 1618)	N/A
Week 236OLP	1660	(1619 - 1702)	N/A
Week 248OLP	1744	(1703 - 1786)	(1577 - 1912)
Week 260OLP	1828	(1787 - 1870)	N/A
Week 272OLP	1912	(1871 - 1954)	N/A
Week 284OLP	1996	(1955 - 2038)	N/A
Week 296OLP	2080	(2039 - 2122)	(1913 - 2248)
Week 308OLP	2164	(2123 - 2206)	N/A
Week 320OLP	2248	(2207 - 2290)	N/A

8. Safety Analyses

AEs will be recorded from the time written informed consent is signed through the 90-day safety Follow-up visit to ensure adequate collection of adverse events that could be associated with investigational drug.

Treatment-emergent adverse events include adverse events that started between the date of first dose of OLP and 90-day safety Follow-up visit after the date of last dose.

9. Guideline on Missing Date Imputation

The following missing data imputation rules will be applied to the OLP analyses.

Medication Dates:

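### Read literally, the open-label addendum's 1 mg entry rule leaves patients who stop during the first-week dose escalation out of its OLP ITT and OLP Safety cohorts

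*SAP*

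**What the plan says.** Addendum Section 3 sets up two OLP cohorts. The ITT cohort is "labeled by randomized treatment in the parent study for all subjects who received at least one dose of RPC1063 1mg in OLP". The Safety cohort is labelled by the treatment actually received and covers "all subjects who received east one dose of RPC1063 1mg in OLP"; the word east is plainly a damaged at least.

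The OLP does not begin at 1 mg. Protocol Section 9.1 states: "There will be an 8-day dose escalation regimen consisting of 4 days of treatment with RPC1063 0.25 mg", then 3 days of 0.5 mg, then 1 mg. SAP v2.0 Section 4 gives the same sequence. It applies to every OLP patient, whatever the earlier arm.

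Other places use a wider rule:
- Addendum Section 8: "Treatment-emergent adverse events include adverse events that started between the date of first dose of OLP", with no strength named.
- Protocol Section 13.5: "The Safety population will consist of all patients receiving any investigational drug".
- SAP v2.0 Section 6.8 bases its Safety population on receipt of any study treatment, and Section 5.4 defines study drug as the assigned capsules "as well as the titration doses".
- Addendum Section 5 bases disposition on participation in the OLP, without a 1 mg condition.

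Addendum Section 7 summarizes OLP efficacy in the OLP ITT population, with NRI as the primary method for missing binary outcomes.

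**The concern.** A cohort that starts at the first 1 mg capsule requires the patient to have stayed on drug for a week. That is selection on something that happens after treatment starts, and it can only remove patients who did poorly enough, or were unwilling enough, to stop early.

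For safety, the week in question is the one the protocol watches most closely. Section 11.5 describes bradycardia and first-degree AV block as mainly first-dose effects in fingolimod studies. Tables 2 and 4 put the hourly vital signs, the ECGs and the 24-hour Holter recording on the first OLP day. The text after Table 4 allows no dose adjustment and requires withdrawal of patients who cannot tolerate the drug, so stopping in that week is possible. For former placebo patients it is also the first exposure to RPC1063.

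For efficacy, the purpose of NRI is to count patients who leave early as failures. An entry rule that removes them beforehand works against that purpose.

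**Working it through.** **Step 1. When 1 mg is first taken.** Input: "4 days of treatment with RPC1063 0.25 mg, followed by 3 days of treatment with RPC1063 0.5 mg, followed by RPC1063 1 mg" (protocol Section 9.1). First 1 mg day = 4 + 3 + 1 = Day 8, which reproduces the stated 8-day escalation. The visit schedule agrees. Weeks are counted from the end of escalation, so Week 4OLP = 8 + 28 = Day 36 and Week 8OLP = 8 + 56 = Day 64 (protocol Table 2), while Week 20OLP = 8 + 140 = Day 148 and Week 56OLP = 8 + 392 = Day 400 (addendum Section 7.3). Missed doses could only move the first 1 mg dose later.

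**Step 2. Event window against cohort entry.** The treatment-emergent window opens on Day 1 and cohort eligibility on Day 8, a gap of 7 dosing days. A patient who stops within the gap can have treatment-emergent events under addendum Section 8 without belonging to the cohort that would tabulate them. A patient who has an event on Day 1 but continues to Day 8 is in the cohort, and that event is counted.

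**Step 3. Effect on an NRI rate.** Let N be the patients dosed in the OLP, e those who stop on Days 1-7, and R the responders. The earliest efficacy window in addendum Section 7.3 opens on Day 19, so a first-week assessment maps to no visit. I assume early stoppers have no later efficacy assessment, so none is in R. The any-dose rate is R/N and the literal-rule rate is R/(N - e). The increase is (R/N) × e/(N - e).

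The documents give none of N, e or R. Assumed ranges: N = 100 to 180, stopping of about 1% to 5% (rounded to whole patients), and an any-dose response of 30% or 50%.

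| N | e | 30% response: literal rate (increase) | 50% response: literal rate (increase) |
|---|---|---|---|
| 100 | 1 | 30/99 = 30.3% (+0.30) | 50/99 = 50.5% (+0.51) |
| 100 | 5 | 30/95 = 31.6% (+1.58) | 50/95 = 52.6% (+2.63) |
| 150 | 2 | 45/148 = 30.4% (+0.41) | 75/148 = 50.7% (+0.68) |
| 150 | 8 | 45/142 = 31.7% (+1.69) | 75/142 = 52.8% (+2.82) |
| 180 | 2 | 54/178 = 30.3% (+0.34) | 90/178 = 50.6% (+0.56) |
| 180 | 9 | 54/171 = 31.6% (+1.58) | 90/171 = 52.6% (+2.63) |

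The increase runs from about 0.3 to 2.8 percentage points. The top value comes from 8 of 150, which is 5.3% after rounding. With e = 0 there is no change.

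**The case against.** The strongest reply is that 1 mg names the whole OLP regimen. Protocol Section 9.1 says OLP patients receive 1 mg daily and then describes the escalation as part of that treatment. The randomized 1 mg arm likewise includes its own escalation days. On that reading the cohort is everyone dosed in the OLP, and Sections 3 and 8 of the addendum agree. This may well be what was intended. But the visible text of the addendum does not say so, and SAP v2.0 Section 5.4 lists the titration doses in addition to the 1.0 mg capsule. A programmer could reasonably set the flag by capsule strength. The addendum's introduction and study design sections have no visible text in the public copy, so a clarification there cannot be ruled out.

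A second reply is that protocol Section 13.5 and SAP v2.0 Section 6.8 define whole-study populations, and the addendum adds OLP cohorts without redefining them. That stands. The sharper conflict is inside the addendum, between Sections 3 and 8.

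A reader might also infer that no OLP output could show a patient who stopped in the first week, or that all such patients' adverse events would vanish. The documents do not support either:
- Disposition covers all OLP participants (addendum Section 5), and SAP v2.0 Section 6.11 tabulates withdrawals and reasons by period.
- No visible text withdraws the v2.0 Safety population, its OLP adverse event tables, or the complete listings of adverse events, serious events and events leading to discontinuation (SAP v2.0 Sections 6.8, 6.20 and 6.20.1).

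Nor do the documents show that early stoppers are mainly patients with cardiac first-dose events. Protocol Section 11.5 calls those effects transient and reversible, and Table 4 responds to findings at 6 hours with further observation.

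**Conclusion.** The definition is wrong as written: taken literally, it keeps patients exposed only to escalation doses out of both OLP cohorts, and it does not fit the addendum's own event window. The loss is confined to the addendum's OLP safety-cohort summaries and its NRI denominators. It does not extend to disposition, the v2.0 Safety-population outputs or the listings.

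The size cannot be derived from the documents. The 0.3 to 2.8 point range rests entirely on the assumed entrants, stopping fraction and response rate. If nobody stopped in the first week, or if 1 mg was meant as a regimen label and programmed that way, nothing changes. The possible omission from the safety summaries matters more than the shift in response rates.

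OLP efficacy is uncontrolled and descriptive, safety results are not tested, and the primary and Week 8 key secondary analyses are unaffected. The point should be fixed, but it is not critical to the trial's conclusions.

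**What to change.** In addendum Section 3, define both the OLP ITT and the OLP Safety cohort as subjects who received at least one dose of RPC1063 of any strength in the OLP, escalation doses included. Cohort entry then starts on the same day as the treatment-emergent window in Section 8, and it is consistent with protocol Section 13.5 and SAP v2.0 Sections 5.4 and 6.8.

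The cost is one phrase and one population flag. Dosing and data collection are untouched. OLP response and early-discontinuation rates may look slightly less favourable. If the regimen reading was intended, no result changes and the text simply says what was meant.
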